4.3.2 Secondary Performance Endpoints

The difference between two groups will be examined by using ANCOVA adjusting for site and baseline opacity grade. Display of ANCOVA results in summary tables will contain difference between LS Means, a one-sided p-value <0.05 will conclude superiority.

4.4 Multiplicity Strategy

A sequential (closed) testing procedure will be used to control type I error rate due to multiplicity for primary and secondary endpoints at one-sided 0.05 significance level.

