# INTREPID® Balanced Ultrasound (u/s) Tip

The INTREPID® Balanced u/s tip [510(K) Number K911808] minimizes energy along the shaft area that interfaces with the incision while maximizing energy at the cutting edge. Since the u/s tip creates up to 190 microns of tip movement at 100% amplitude as compared to 130 micron of movement of the Mini Flared Kelman (MFK) tip, the amplitude is normally lowered to 60% amplitude to achieve equivalent cutting. The Balanced tip cuts in a superior fashion to the Mini Flared Kelman tip. Coupled with the INTREPID® Ultra Infusion sleeve, less energy is dissipated in the incision.

A previous Alcon-sponsored study (Clinicaltrials.gov identifier: NCT01848288) showed lower Cumulative Dissipated Energy (CDE), Aspiration Time and Aspiration Fluid Used for the Centurion® (K121555) with the Balanced tip vs the Infiniti® with a Mini Flared Kelman tip.

This study is designed to determine if Centurion® Vision System enhancements translate to a more efficient cataract procedure as defined by CDE and BSS fluid use.

Document: TDOC-0050176 Version: 2.0; Effective; CURRENT

Status: Effective Page 21 of 75

Both the Centurion® (K121555) and Infiniti® (K112425, K120912) Vision Systems and the INTREPID® Balanced Tips and the MFK Tips are US FDA cleared and CE marked, and will be used as per the label indications. No new risks are introduced with the use of the either the Centurion® or the Infiniti®. As with any type of cataract surgery with intraocular lens implantation, there is a possibility of complications due to anesthesia, drug reactions, and surgical problems. Potential risks /surgical complications associated specifically to the phacoemulsification cataract procedure include the following:

- capsular injury
- thermal burns
- vitreous loss
- persistent corneal edema

A summary of known and potential risks and benefits to humans, as identified in the literature or through preclinical testing and/or prior clinical evaluations, for each investigational product can be found in the Directions for Use and Operator's Manual for the Centurion® Vison System and the Infiniti® Vision System.

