# 9.3 Rationale for Study Design

The Centurion® Vision System incorporates Active Fluidics™ control system that maintains a stable surgical IOP despite variations in aspiration flow rate. A more stable surgical IOP allows the surgeon to experience less movement of ocular structures, as well as safely lower the surgical IOP. This coupled with the higher resistive aspiration tubing coupled with lower compliant aspiration tubing and Active Fluidics™ minimize occlusion break surge. The

Document: TDOC-0050176 Version: 2.0; Effective; CURRENT

Status: Effective Page 29 of 75

system is capable of creating significantly higher vacuum levels (~20% higher than the Infiniti® Vision system) which creates higher tip holding forces.

Previous Alcon-sponsored study (M-13-006, Data on File) have also shown that the Centurion with the 45° Balanced u/s tip used significantly less CDE than the Infiniti with the 45° MFK tip. At 100% amplitude, the Balanced tip creates 190  $\mu$ m stroke vs 130  $\mu$ m stroke for the MFK tip. The Centurion amplitude is normally set at 60% max and the Infiniti at ~90% max. CDE is therefore reduced by 33%.

This study has been designed to obtain a better understanding of how both the Centurion® and the Balanced Tip affect CDE and BSS fluid used, as well as assess the correlation to  $\Delta$ CCT and  $\Delta$ ECD.

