## 15.10 Sample Size Justification

Based on previous studies, a sample size of 53 in each group will have 80% power to detect a difference in means of -7.4 (the difference between a Group 1 mean of 38.5 and a Group 2 mean of 45.9).

Print Date: Print Date:

Document: TDOC-0050176 Version: 2.0; Effective; CURRENT

Status: Effective Page 63 of 75

Assuming that the common standard deviation is 15.2 using a two group t-test with a 0.05 one-sided significance level.

Assuming a 10% dropout rate, 59 subjects per group (up to 177 in total) will be randomized.

**Document:** TDOC-0050176 **Version:** 2.0; Effective; CURRENT

Status: Effective Page 64 of 75

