1.1 Study Objectives

PRIMARY OBJECTIVE

Demonstrate that the Centurion® Vision System used with the 45° Balanced tip will result in less Cumulative Dissipated Energy (CDE) than the Infiniti® Vision System used with the 45° Mini-Flared Kelman (MFK) tip during cataract extraction surgery via phacoemulsification of cataract grades NII- NIV (LOCSII).

SECONDARY OBJECTIVES

- 1). Demonstrate that the Centurion® Vision System used with the 45° Balanced tip will result in less CDE than the Centurion® Vision System used with the 45° MFK tip during cataract extraction surgery via phacoemulsification of cataract grades NII-NIV (LOCSII).
- 2). Demonstrate that the Centurion® Vision System used with the 45° Balanced tip will result in less BSS Fluid Used than the Infiniti® Vision System used with the 45° MFK tip during cataract extraction surgery via phacoemulsification of cataract grades NII-NIV (LOCSII).
- 3). Demonstrate that the Centurion® Vision System used with the 45° MFK tip will result in less BSS Fluid Used than the Infiniti® Vision System used with the 45° MFK tip during cataract extraction surgery via phacoemulsification of cataract grades NII-NIV (LOCSII).
- 4). Demonstrate that the Centurion® Vision System used with the 45° MFK tip will result in less CDE than the Infiniti® Vision System used with the 45° MFK tip during cataract extraction surgery via phacoemulsification of cataract grades NII- NIV (LOCSII).

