4.2.2 Hypothesis for the Secondary Endpoints

The null and alternative hypotheses for the secondary analyses are:

Secondary hypotheses 1

$$H_0: \mu_{\text{centurion_Bal CDE}} \geq \mu_{\text{centurion_MFK CDE}}$$

$$H_A: \mu_{\text{centurion_Bal CDE}} < \mu_{\text{centurion_MFK CDE}}$$

Where $\mu_{\text{centurion_Bal CDE}}$ and $\mu_{\text{centurion_MFK CDE}}$ are the true mean values of the secondary endpoint, CDE under Centurion® with the Balanced tip, and Centurion® with the MFK tip, respectively.

Secondary hypotheses 2

$$H_0: \mu_{\text{centurion_Bal BSS}} \geq \mu_{\text{Infiniti_MFK BSS}}$$

$$H_A: \mu_{\text{centurion_Bal BSS}} < \mu_{\text{Infiniti_MFK BSS}}$$

Where $\mu_{\text{centurion_Bal BSS}}$ and $\mu_{\text{Infiniti_MFK BSS}}$ are the true mean values of the secondary endpoint, BSS under Centurion® with the Balanced tip, and Infiniti® with the MFK tip, respectively.

Secondary hypotheses 3

$$H_0: \mu_{\text{centurion_MFK BSS}} \geq \mu_{\text{Infiniti_MFK BSS}}$$

$$H_A: \mu_{\text{centurion_MFK BSS}} < \mu_{\text{Infiniti_MFK BSS}}$$

Where $\mu_{\text{centurion_MFK BSS}}$ and $\mu_{\text{Infiniti_MFK BSS}}$ are the true mean values of the secondary endpoint, BSS under Centurion® with the MFK tip, and Infiniti® with the MFK tip, respectively.

Secondary hypotheses 4

$$H_0: \mu_{\text{centurion_MFK CDE}} \geq \mu_{\text{Infiniti_MFK CDE}}$$

$$H_A: \mu_{\text{centurion_MFK CDE}} < \mu_{\text{Infiniti_MFK CDE}}$$

Where $\mu_{\text{centurion_MFK CDE}}$ and $\mu_{\text{Infiniti_MFK CDE}}$ are the true mean values of the secondary endpoint, CDE under Centurion® with the MFK tip, and Infiniti® with the MFK tip, respectively.

[figure not shown]

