5.4 Interim Analysis for Safety

Not Applicable.

6 Sample Size and Power Calculations

Based on previous studies, a sample size of 53 subjects in each procedure group will have a 80% power to detect a mean difference of -7.4 percent-seconds in CDE between the two procedure groups (Centurion® with the 45° Balanced tip minus Infiniti® with the MFK tip) using a two-sample t-test with a one-sided 5% level of significance, assuming a common standard deviation of 15.2.. Assuming a 10% dropout rate, 59 subjects per procedure group (up to 177 in total) will be randomized.

7 References

See protocol Section 17 for details.

8 Revision History

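### Does the sequential testing plan leave the console comparison of CDE (secondary hypothesis 4) with almost no chance of success?

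*SAP*

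**What the plan says.** SAP 4.4 and Protocol 15.6 give the same single sentence on multiplicity: "A sequential (closed) testing procedure will be used to control type I error rate due to multiplicity for primary and secondary endpoints", at a one-sided 0.05 level. Neither section writes out a testing order or a stopping rule. The secondary objectives (Protocol 8.2, SAP 1.1) and hypotheses (Protocol 15.4.2.1, SAP 4.2.2) carry the same numbers 1 to 4:

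- S1: CDE, Centurion Balanced against Centurion MFK (tip effect on one console).
- S2: BSS, Centurion Balanced against Infiniti MFK.
- S3: BSS, Centurion MFK against Infiniti MFK.
- S4: CDE, Centurion MFK against Infiniti MFK (console effect with one tip). The objective reads "Demonstrate that the Centurion® Vision System used with the 45° MFK tip will result in less CDE than the Infiniti® Vision System" with the same tip.

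Only the primary comparison is sized. SAP 6 states that 53 per group "will have a 80% power to detect a mean difference of -7.4 percent-seconds in CDE between the two procedure groups", and names Centurion Balanced minus Infiniti MFK as the pair. Protocol 15.10 agrees: "a sample size of 53 in each group will have 80% power to detect a difference in means of -7.4". No effect, SD or power is given for S1 to S4.

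**The concern.** Protocol 7.1 describes the study as "designed to determine if Centurion® Vision System enhancements translate to a more efficient cataract procedure as defined by CDE and BSS fluid use", and the rationale in Protocol 9.3 begins "This study has been designed to obtain a better understanding of how both the Centurion" and goes on to name the tip as well. S4 is the only CDE test of the console with the tip held fixed. If the numbers are the testing order, S4 comes last, behind a tip test, and both of those tests draw on a total effect that the trial is only just large enough to detect as a whole. S1, which has no stated power, also stands in front of both BSS objectives.

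A real console effect could therefore go unclaimed. If the tip added nothing, S1 would be a true null and the chain would end there in about 95% of trials, however large the console effect. SAP 4.3 asks for an LS-mean difference and a p-value and names no interval, so a comparison that is not reached might seem to leave little to interpret.

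**Working it through.** **Inputs.** Difference -7.4, SD 15.2, 53 evaluable per arm, one-sided 0.05 (SAP 6, Protocol 15.10); 59 per arm randomized; 1:1:1 allocation (SAP 1.2).

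**1. The plan's own figure.** SE = 15.2 × √(2/53) = 2.953. Then 7.4/2.953 = 2.506, and 2.506 - 1.645 = 0.861, which gives 80.5% power by the normal formula and 80.1% by the exact t. For dropout, 53/0.9 = 58.9, rounded up to 59. The stated sample size is reproduced.

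**2. The constraint.** (Centurion Balanced - Centurion MFK) + (Centurion MFK - Infiniti MFK) = Centurion Balanced - Infiniti MFK. So the S1 and S4 true differences sum to the primary difference. Their estimates share the Centurion MFK arm with opposite signs, so they correlate at -0.5. If both reject, the primary estimate is at least 2 × 1.645 × 2.953 = 9.7 in the favourable direction, so in this normal model the primary rejects too.

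**3. Numbered order with a stop.** The tip's share of the -7.4 is not in the documents, so the full range is shown. Both BSS tests are taken as always passing, so the S4 column is an upper bound.

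| Tip share | S1 power alone | BSS tests reached (primary and S1 reject) | Primary, S1 and S4 all reject |
|---|---|---|---|
| 0% | 5% | 4.9% | 2.1% |
| 25% | 15% | 15% | 4.3% |
| 50% | 35% | 33% | 5.4% |
| 75% | 59% | 53% | 4.3% |
| 100% | 81% | 69% | 2.1% |

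The peak is at the even split: 5.35% by bivariate normal, 5.4% by simulation with t critical values.

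**4. How firm that ceiling is.** It moves with three inputs.

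- Sample size: CDE is read at the end of surgery (Protocol 12.1.2.6.1), and the ITT set is everyone randomized who has the procedure (SAP 2.1). Later dropout removes no CDE values, so n can be near 59, where the ceiling is 6.7%.
- Covariates: the test is an ANCOVA with opacity grade, and the synopsis says harder lenses need more CDE. The gain is not stated. An assumed R² of 0.3 gives 11.4% (n = 53) or 14.2% (n = 59); 0.5 gives 22.2% or 26.9%.
- True effect: totals of -10, -12 and -15.1 give at most 19%, 36% and 64% (n = 53). The last is 33% of 45.9, after the statement in Protocol 9.3 that "CDE is therefore reduced by 33" per cent.

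**5. Sequence or power?** At the even split, S4 has 34.8% power with no gate at all, because 3.7/2.953 = 1.253 and 1.253 - 1.645 = -0.392. Placed directly after the primary, it is claimed in about 32% of trials. For 80% power on a difference of 3.7, about 210 per arm would be needed. No ordering makes S4 well powered at that split.

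**6. Error rate.** If the S1 and S4 nulls both hold, so does the primary null. Simulated family-wise error is about 5% in the numbered order.

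**The case for a change.** The strongest argument for a change is that S4 could be freed from S1 at no cost in alpha: once the primary null is false, the S1 and S4 nulls cannot both be true, so the two could be tested side by side at 0.05. That logic is correct. One order that uses it is primary, S2, S3, then S1 with S4. Assume 80% power for each BSS contrast and a CDE-BSS correlation of 0.3; neither figure is in the documents. At an even split, S4 then rises from about 4% to 26% and S2 from 28% to 67%.

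The gain is paid for elsewhere. S1 falls from 33% to 23% at the even split, and from 69% to about 50% when the tip carries the whole effect. That order also makes S1 depend on two BSS tests with no stated power. If the console does not reduce BSS use, S1 drops to about 3% even at full tip share. One unsized gate is exchanged for two.

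The case of a tip that adds nothing also stands as arithmetic, but it runs against the plan's rationale. Protocol 7.1 claims better cutting for the Balanced tip, and Protocol 9.3 derives its CDE reduction from amplitude settings. On that mechanism S1 passes easily and the gate costs little. If the tip carries the whole effect, S4 is a true null, which should rarely be claimed. Protocol 7.1 also links higher vacuum to lower CDE, so a console effect is not ruled out, and putting the tip test first remains a judgement.

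On intervals, SAP 4.3 says what the tables will contain. It does not say that nothing else may appear, or that estimates are withheld when testing stops. The ANCOVA yields a standard error for every contrast, so a 90% interval for S4 (half-width about 1.645 × 2.953 = 4.9) is available in routine reporting.

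**Conclusion.** No change follows. The identity and the ceiling are right: with the numbered order and a stop, S4 is claimed in at most about 5% (n = 53) to 7% (n = 59) of trials. Those figures assume a true total of exactly -7.4, no covariate gain and BSS tests that always pass; a larger effect or useful covariates raise the ceiling considerably.

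The unwritten order is a gap that analysts fill sensibly. The numbering is the same in the objectives and hypotheses of both documents, and following it with a stop controls the family-wise error at one-sided 0.05. Power is promised only for the primary comparison, and that promise is kept. A low chance for the last of four unsized secondaries is a matter of priority. Giving S4 a better place costs S1 power, or ties S1 to unsized BSS tests. The choice between tip and console is a fair trade-off for the sponsor. The primary test, its alpha, the sample size and the success rule are unaffected. A reader should simply not take a failed or untested "Secondary hypotheses 4" as evidence that the console has no effect on CDE.

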4.5 Subgroup Analyses and Effect of Baseline Factors

Not applicable.

4.6 Interim Analysis for Performance

Not applicable.

4.7 Handling of Missing Data

No imputation technique will be performed on missing values.

5 Safety Analysis Strategy

5.1 Safety Endpoints

The safety endpoints are:

- Adverse events (including Secondary Surgical Interventions (SSIs))
- Slit-lamp examination findings (clinical observations)
- Anterior chamber cells
- Anterior chamber flare
- Corneal edema
- Endothelial cell count
- Dilated fundus examination findings (clinical observations)
- Best corrected distant visual acuity (BCDVA)
- Intraocular pressure (IOP)
- Problems during surgery
- IOL placement
- Device deficiencies

Analysis for the anterior chamber cells, anterior chamber flare and endothelial cell counts will be presented in the performance analysis section.

5.2 Safety Hypotheses

There are no formal safety hypotheses in this study.

5.3 Statistical Methods for Safety Analyses

Safety analyses will be conducted using the safety analysis set on a treatment-emergent basis. The safety analysis set will include all subjects exposed to the investigational procedure. For treatment-emergent safety analyses, subjects will be categorized under the actual treatment received. Subjects exposed to an incorrect study treatment for the entire treatment period will be included in the group corresponding to the treatment received. Subjects exposed to an incorrect study treatment for a portion of the treatment period will be accounted for under the actual treatment the subject was first exposed to in the study.

Analysis of the safety endpoints will include descriptive statistics for each parameter by procedure group. Descriptive statistics generated for safety parameters will be based upon the type of parameter (i.e., whether the data are categorical or continuous) being analyzed. For categorical parameters, the statistics used to summarize the data descriptively will include sample size, number in the category and percent in the category. For continuous parameters, sample size, mean, median, standard deviation, minimum and maximum, etc. will be presented.

Listings describing details of adverse events will be provided. Listings describing details of adverse events reported prior to the surgery will be presented separately from the safety analysis.

5.3.1 Adverse Events

AEs will be coded by Medical Dictionary for Regulatory Activities (MedDRA). All AEs occurring from when a subject signs informed consent to when a subject exits the study will be accounted for in the reporting. A treatment-emergent AE is an event not present prior to exposure to investigational product or any pre-existing event that worsens following exposure to investigational product.

Descriptive summaries (counts and percentages) for specific AEs will be presented by System Organ Class (SOC) and Preferred Term (PT). In addition to an overall presentation of all AEs, if applicable, reports will be generated for special classes of AEs such as most, ocular AEs, non-ocular AEs, investigational product-related AEs, serious AEs, and AEs resulting in treatment discontinuation. Relatedness and severity will be presented for each AE entry. These reports will be supported by individual subject's listings, as necessary.

Only subject listings will be provided for AEs that occur after signing informed consent but prior to exposure to investigational procedure. These listings will comprise all events occurring during this period in any subject who consented to participate in the study.

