	Phaco-emulsification of a harder lens requires more CDE and more BSS fluid. For this study, the softest lenses (LOCSII Opacities N0 and NI) will be excluded, leaving all lenses with LOCSII Opacities NII-NIV.	
	For each group, cataract surgery will be performed on subjects who will be randomized with an equal number having their surgery performed with each configuration.	
	Clear Cornea Incision: 2.2mm-2.4mm	
	Approximately 177 subjects (59 per group) randomized with an	
No. of Subjects:	expectation to have at least 159 completed subjects (53 per group) for evaluability.	
Region(s):	Approximately 5 investigational sites across the USA, LACAN, Asia-Pacific and EMEA	
Clinical Trial	a) Total expected duration of clinical investigation: approximately	
Duration:	12 months	
	b) Expected duration of each subject participation: up to 5 months c) Planned follow-up duration for each subject: up to 3 months	
	postoperative	
	d) Estimated subject recruitment period (time needed to select the number of patients): approximately 6 months	

Document: TDOC-0050176 Version: 2.0; Effective; CURRENT

Status: Effective Page 5 of 75

Clinical Trial Population:	Adult subjects of 21 years of age and above requiring cataract extraction followed by IOL implantation. Nuclear Opalescence II to IV using LOCS II.	
Treatments:	Test Article:	Centurion ® Vision System - version 2.04 45°Balanced Tip   Used with INTREPID ® Ultra Infusion Sleeve
	Administration:	Surgical instrumentation
	General Description:	Centurion ® Vision System (v2.04) will be used with the 45° Balanced Tip (coupled with the INTREPID ® Ultra Infusion sleeve) for phaco-emulsification procedure.
	Duration of Treatment:	One time routine surgical procedure followed by 3 months (+/- 14 days) of postoperative follow-up.
	Control Article:	Centurion ® Vision System (version 2.04) with 45° Mini Flared Kelman u/s Tip  (with INTREPID ® Ultra infusion sleeve)  Infiniti ® Vision System (version 3.01) with
		45° Mini Flared Kelman u/s Tip   Used with INTREPID ® Ultra Infusion Sleeve  Used with Ultra infusion Sleeve
	Administration:	Surgical instrumentation
	General Description:	Centurion® Vision System (version 2.04) will be used with the 45° Mini Flared u/s Tip coupled with INTREPID® Ultra infusion sleeve) for phaco-emulsification procedure.

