Randomization*	X					
Adverse Events (Including Secondary Surgical Intervention)	X	X	X	X	X	X
Device Deficiencies		X				
Complete Exit Form 					X	X

<sup>1 If a subject exits early, the Visit 3 procedures should be performed at the last available visit, if at all possible

Print Date: Printed By:

<sup>2 Only BCDVA Visual Acuity to be completed at 6-Month Safety Follow-up visit \*Randomization should be completed within 2 working days prior to the date of surgery

\*\*6-Month Safety Follow-up Visit (if required). See section 12.1.6 Additional 6-month Safety Follow-up Visit

Document: TDOC-0050176 Version: 2.0; Effective; CURRENT

Status: Effective Page 20 of 75

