#### 9.5 Risk Benefit Assessment

Both the Centurion® (K121555) and Infiniti® (K112425, K120912) Vision Systems and the INTREPID® Balanced Tips and the MFK Tips are US FDA cleared and CE marked, and will be used as per the label indications. No new risks are introduced with the use of the either the CVS or the IVS. As with any type of intraocular surgery, there is a possibility of complications due to anesthesia, drug reactions, and surgical problems. Potential risks / surgical complications associated specifically to the phacoemulsification cataract procedure include the following:

- capsular injury;
- thermal burns;
- vitreous loss; and
- persistent corneal edema.

Additional subject discomforts may include pupil dilation and the use of numbing eye drops. There is an additional subject burden of one non-standard postoperative visit (Visit 3).

Print Date:

**Document:** TDOC-0050176 **Version:** 2.0; Effective; CURRENT

Status: Effective Page 30 of 75

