## 12.1.6 Additional 6-Month Safety Follow-up Visit

Subjects who have completed the 3 month visit with an ECD count of less than 1500 cells/mm^2 and/or a decrease in ECD of 20% or more (in comparison to the screening visit value) at their 3 month visit, must return 3 months later for a 6 month safety follow-up visit.

The following safety assessments are to be performed at the 6-Month Safety Follow-up visit:

- A repeat ECD assessment
- Visual Acuity BCDVA
- Slit lamp examination corneal edema
- \_
- Any other assessment performed as standard of care at the site

Subject data from the additional safety assessments will be captured in the electronic database, accordingly.

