#### 12.4 Unscheduled Visit

After signing ICF, if a subject requires a study eye visit that is not specified in the protocol, the visit is considered an Unscheduled Visit (UNSV). For the 6-Month Safety Follow-up Visit please refer to Section 12.1.6.

Study eye ocular examinations conducted by non-study personnel are not considered an UNSV. Also, Pre-planned, routine postoperative visits (eg, 1-month postoperative visit) are not considered unscheduled visits unless an AE (serious or non-serious) is reported and study personnel are involved in the conduct of the visit.

**NOTE:** Any AE (serious or non-serious) arising from a pre-planned, routine postoperative visit must be captured and reported as in accordance with Section 13: Device Deficiencies and Adverse Events regardless of study personnel involvement.

During an unscheduled visit, it is recommended that the following information be collected:

- Concomitant medications
- Visual acuity (UCDVA, BCDVA)
- Slit-lamp exam
- Conjunctival edema grading
- Wound leakage
- Fundus exam
- IOP

**Document:** TDOC-0050176 **Version:** 2.0; Effective; CURRENT

Status: Effective Page 47 of 75

Adverse events and device deficiencies

Activities undertaken during an UNSV should be collected in accordance with this protocol and the MOP. Data collected will be entered into EDC.

If the subject is discontinued at the unscheduled visit, all Early Exit procedures should be performed. Refer to *Section 6 SCHEDULE OF VISITS*. If an UNSV is required after the final study visit for safety purposes, the data will not be captured in EDC. Refer to *Section 13.5 Follow-Up of Safety Information*.

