8.2 Revisions for Version 3.0

The following revisions were made to Version 3.0 of the Statistical Analysis Plan to correct the calculation for Estimated Incision Leakage and to provide clarification on how endothelial cell density data would be analyzed.

In Section 1.1, the sentences:

[REDACTED]

*BSS Used for Centurion = (Bag Weight after Prime)-(Bag Weight after surgery) – 0.5ml

*BSS Used for Infiniti = (Bottle Weight after prime)-((Bottle weigh after Surgery)

[REDACTED]

were changed to

[REDACTED]

*BSS Used for Centurion = (Bag Weight after Prime) – (Bag Weight after Surgery) – 0.5ml

*BSS Used for Infiniti = (Bottle Weight after prime) – (Bottle Weight after Surgery)

[REDACTED]

In addition, the following sentences were added to Section 4.2:

Up to three specular microscopy images will be taken of the study eye at Visit 0 and Visit 3. The mean of the up to three values for endothelial cell density, coefficient of variation and percent hexagonal cells, rounded to one decimal place, will be used in the analyses.

9 Appendix

Table 11.-1 Schedule of Visits

Activity	Visit 0 (-60 to 0 d)	Visit 00 (0 d)	Visit 1 (1 d)	Visit 2 (7 +/- 2 d)	Visit 3 (90 +/- 14d)
	Unilateral examination				
Informed Consent	X				
Demographics	X				
Medical History	X	X			
Concomitant Medications	X	X	X	X	X
Inclusion/Exclusion	X	X			
Surgery		X			
Problems During Surgery		X			
Other Procedures at Surgery		X			
Lens Information		X			
IOL Placement		X			
Programmable Phacoemulsification Settings			X		
Phacoemulsification Metrics (Including CDE, BSS Fluid Use, [REDACTED])			X		
Visual Acuity (UCDVA & BCDVA)	X			X	X
Intraocular Pressure	X		X	X	X
Specular Microscopy	X				X
[REDACTED]	X		X	X	
Slit Lamp Examination	X		X	X	X
Crystalline Lens Assessment	X				
Anterior chamber cells and flare	X		X	X	X
Dilated Fundus Examination	X				X
Randomization*	X				
Adverse Events (Including Secondary Surgical Intervention)	X	X	X	X	X
Device Deficiencies		X			
Complete Exit Form ¹					X

If a subject exits early, the Visit 3 procedures should be performed at the last available visit, if at all possible.

*Randomization should be completed within 2 working days prior to the date of surgery.

Date/Time (mm/dd/yyyy GMT):	Signed by:	Justification:

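### Does leaving study exit undefined for subjects who need the 6-month safety visit distort the adverse event tables by arm?

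*SAP*

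**What the plan says.** SAP 5.3.1 covers all AEs "from when a subject signs informed consent to when a subject exits the study will be accounted for in the reporting". Its treatment-emergent definition has a start (exposure) and no end, so exit is the only upper limit on the count.

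SAP 1.2 lists five visits, the last at Day 90 +/- 14. The schedule in the SAP Appendix has no later column, marks the exit form only at Visit 3, and carries the footnote "If a subject exits early, the Visit 3 procedures should be performed at the last available visit, if at all possible".

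Protocol Section 6 has one more column, the 6-Month Safety Follow-up Visit. The row "Complete Exit Form" is marked there and at Visit 3, and so is the adverse events row. Under Protocol 12.1.6, a subject with ECD below 1500 cells/mm² and/or a loss of 20% or more at month 3 "must return 3 months later for a 6 month safety follow-up visit", and the data go into the database.

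Protocol 12.4 adds, for unscheduled visits: "If an UNSV is required after the final study visit for safety purposes, the data will not be captured in EDC". The synopsis still gives "Planned follow-up duration for each subject: up to 3 months".

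**The concern.** For a subject who meets the ECD criterion, neither document says whether the visit that closes the AE count is Visit 3 or the 6-month visit. Each answer appears to do harm.

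- If exit is Visit 3, AEs that the protocol asks sites to record at 6 months lie outside the SAP's reporting window.
- If exit is the 6-month visit, these subjects are observed for about 180 days and the others for about 90. The criterion is met after randomization. Protocol 9.3 says the study is to show how the machine and tip "affect CDE and BSS fluid used, as well as assess the correlation to" the change in ECD, so the proportion meeting it could differ by arm. The AE percentages would then compare unequal follow-up.

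Protocol 12.4 depends on the same undefined point. ECD images go to a reading center, so a site may complete the Visit 3 exit form before it knows that the subject must come back.

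**Working it through.** **Inputs.** Randomized per arm: 59 (SAP Section 6). The plan's own figure reproduces: a one-sided 5% t-test with 80% power, difference 7.4 and SD 15.2 needs 52.86, so 53 per arm, and 53 / 0.90 = 58.9, so 59. The documents give neither the proportion p meeting the ECD criterion nor any AE risk, so both are assumed below.

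**1. Length of the window.** Visit 3 is nominally Day 90 and the conditional visit about Day 180. The mean window in an arm is 90 × (1 + p): 94.5 days at p = 5% and 108 days at p = 20%, a ratio of 1.14.

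**2. The calculation that first suggests itself.** Let q be the 90-day AE risk, with a constant hazard, and let the extra 90 days give new first events to subjects meeting the criterion. The percentage with at least one AE is then q + p × q × (1 − q).

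- q = 10%: 10.45% (p = 5%) against 11.80% (p = 20%), a gap of 1.35 points or 0.80 of 59 subjects.
- q = 30%: 31.05% against 34.20%, a gap of 3.15 points or 1.86 of 59 subjects.

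**3. Why that calculation does not apply.** Protocol 5.1 and 13.1 (specific events) require an AE for every subject who meets the criterion, judged on the month 3 value. Protocol 10.2 names ECD below 1500 among its examples of exclusionary endothelial disease, so the finding is new after surgery and is treatment-emergent under SAP 5.3.1. Every such subject therefore has at least one AE by Visit 3. With s the risk of any AE by Visit 3 among the others, the percentage is p × 1 + (1 − p) × s whichever visit closes the count.

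- s = 10%: 0.05 + 0.95 × 0.10 = 14.5% and 0.20 + 0.80 × 0.10 = 28.0%.
- s = 30%: 0.05 + 0.95 × 0.30 = 33.5% and 0.20 + 0.80 × 0.30 = 44.0%.

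The gaps (13.5 and 10.5 points) come from the assumed difference in ECD loss, which is a real difference between arms. The window contributes 0. The same holds for the percentage with any ocular AE.

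**4. What can still move.** Rows for other preferred terms, and the non-ocular, serious and device-related summaries, can gain subjects. With r the chance of a new AE after Visit 3 in a subject meeting the criterion, the expected number per arm is 59 × p × r.

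- p = 5%, r = 5%: 0.15 subjects.
- p = 20%, r = 10%: 1.18 subjects.
- p = 30%, r = 20%: 3.54 subjects.

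For two arms at p = 5% and 20% with r = 10%, the difference is 1.18 − 0.30 = 0.88 subjects, or 1.5 points of 59, spread over all preferred terms.

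**5. Which exit is meant.** SAP 5.3.1 ties the window to each subject's own exit. A subject who is required to return, to a visit with its own AE and exit form marks, has not left the study at Visit 3. The two marks fit together if the first serves subjects who finish at month 3 and the second those who come back. The SAP Appendix is a visit schedule that lacks the conditional column. It does not define exit.

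**The case for a change.** The best case for a change is that the edit costs almost nothing and the gap is plain. The SAP omits a visit that the current protocol requires, an undefined word sets the AE window, and rows other than the overall and ocular percentages would rest on unequal follow-up. At the 6-month visit sites ask about health since the last visit (Protocol 13.2), so that visit finds AEs in one subgroup only. Protocol 12.4 might also keep data out of the database, which no analyst could restore.

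The mismatch stands as a clerical one. The synopsis shows the same lag: Visit 3 at its latest followed by three more months gives 60 + 104 + 90 = 254 days, about 8.3 months, against a stated participation of up to 5.

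The rest is weaker. Unequal follow-up comes with any conditional safety visit, and early exits cause it too. Cutting the main tables at Visit 3 would equalize the window but take late events out of them, in just the subjects under closer watch. That is a trade-off on which statisticians differ. On lost data, the same question about health since the last visit lets the 6-month visit pick up events from the preceding three months, and Protocol 13.5 tells the investigator to pass new safety information to the sponsor. An event could be missed in the database if the subject also failed to attend at 6 months, but it would still be reportable to the sponsor. Protocol 15.7 lists all AEs, so at most an event's place in a summary table is open.

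**Conclusion.** No change to the plan follows. The SAP schedule was not brought into line with the amended protocol, and exit is not spelled out for subjects with the conditional visit. An analyst would resolve this sensibly by treating exit as the subject's own last required visit, with onset dates available to separate later events.

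The effect on the percentage with at least one AE, overall or ocular, is 0 points, provided sites report the ECD event as the protocol requires. The rest is about 0.15 to 3.5 subjects per arm with additional entries, under assumed rates of 5% to 30% meeting the criterion and 5% to 20% with a later AE. The documents support no narrower range. Carrying the first 90 days' risk forward would probably overstate the count, since that period includes the operation. Safety is descriptive with no hypotheses (SAP 5.2), and the CDE and BSS fluid comparisons use data from the day of surgery, so no conclusion of the trial depends on this point.
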